7.7. Missed Doses

If a dose is missed, the subject should dose as soon as they remember and adjust subsequent doses for that calendar day at 4-hour intervals, resuming protocol-indicated dosing on the next calendar day. Subject will record Date and time of actual dosing in the provided diary.

7.8. Concomitant Therapy

7.8.1. Recording Prior and Concomitant Medications

Any medication or vaccine (including over-the-counter or prescription medicines, vitamins, and/or herbal supplements) that the subject is receiving at the time of enrollment or receives during the study must be recorded along with:

- Reason for use
- Dates of administration including start and end dates
- Dosage information including dose and frequency

The Medical Monitor should be contacted if there are any questions regarding concomitant or prior therapy.

7.8.2. Prohibited Concomitant Medications, Treatments, and Procedures

Subjects must abstain from taking prescription or nonprescription drugs (including topical medications such as ophthalmic solutions [except an ophthalmic solution specially provided by Sponsor, mydriatics, and stain used for trial examinations], nasal drops or spray, vitamins, alternative and complementary medicines [including herbal formulations]) within 14 days or 5 half-lives (whichever is longer) before randomization until completion of the follow-up visit, unless, in the opinion of the investigator and sponsor, the medication will not interfere with the study. Subjects must refrain from use of CYP3A4 inducers, such as St. John's Wort, for 14 days before randomization or at any time during the study. Subjects must abstain from prescribed dry eye medications (e.g. Restasis and Xiidra) for 28 days before randomization or at any time during the study.

7.8.3. Rescue Medicine

No rescue medication will be provided.

7.9. Treatment after the End of the Study

Study medication will not be provided after the end of the study.

8. Discontinuation/Withdrawal Criteria

A subject may voluntarily discontinue participation in this study at any time. It is important to document whether the withdrawal of consent is primarily due to an AE or other reason. The Investigator may also, at his or her discretion, discontinue the subject from participating in this study at any time. Withdrawn subjects will not be replaced.

Subjects may be prematurely discontinued from the study for any of the following reasons:

- Subject non-compliance
- Investigator non-compliance
- Subject requires concurrent prohibited medication during the course of the study. If, in the opinion of the Investigator and the study medical monitor, such medication will not interfere with the conduct or interpretation of the study or compromise the safety of the subject, then the subject may continue to receive study medication. If the subject is discontinued from study medication, they would remain in the study for safety assessments as needed.
- Pregnancy of female subject
- Discontinuation of the study at the request of the Sponsor, regulatory agency or an Institutional Review Board / Independent Ethics Committee
- Grade 3 or 4 clinical AE considered causally related to treatment.

If a subject meets a withdrawal criterion during treatment, procedures listed in the SoA for Part A check-out or Part B Day 29 EOS will be required.

8.1. Discontinuation of Study Treatment

If a clinically significant finding is identified after enrollment, the investigator or qualified designee will determine if the subject can continue in the study and if any change in subject management is needed. Any new clinically relevant finding should be reported as an AE.

Procedures listed in the SoA for Part A check-out or Part B Day 29 EOS should be completed at the time of treatment discontinuation.

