5.3. End of Study Definition

A subject is considered to have completed the study if he/she has completed all phases of the study, ie, Day 2 EOS for Part A and Day 29 EOS for Part B.

The end of the study (EOS) is defined as the date of the last visit for the last subject, including the follow-up telephone call.

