- Slit lamp biomicroscopy w/out mydriatics at 0 hour
- TFBUT at 0 hour
- Corneal fluorescein staining (Baylor) at 0 hour
- Lissamine green staining (Baylor +Lid Margin) at 0 hour
- Intraocular Pressure (iCare tonometer) at 0 hour
- Subjects self-administer study drug at 0, 4, 8, and 12 hours each day
- Subjects record dosing times in diary
- Dispense study drug for administration at home

Day 29 ±2, EOS

- Review AEs and concomitant medications
- DEQ-5 at 0 hour
- VAS at 0, 4, and 8 hours
- OSDI at 0 hour
- MMP-9 at 0 hour (30 minutes before TFBUT and staining tests)
- TFBUT at 0 hour
- Corneal fluorescein staining (Baylor) at 0 hour
- Lissamine green staining (Baylor +Lid Margin) at 0 hour
- Drug administration at 0 hour
- Clinical laboratory tests (hematology, serum chemistry, urinalysis) at 2 hours
- Serum pregnancy test for WOCBP only at 2 hours
- Physical examination, including weight at 4 hours
- Vital signs at 4 hours
- Visual Acuity (Snellen) at 8 hours
- Slit lamp biomicroscopy without mydriatics at 8 hour
- Schirmer I without anesthesia at 8 hours
- Intraocular pressure (iCare tonometer) at 8 hours
- Slit lamp biomicroscopy w/ mydriatics (lens observation) at 8 hours
- Ophthalmoscopy at 8 hours

Day 36 ±2

- Follow-up telephone call to review AEs and concomitant medications

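### Stopping study drug early in Part B triggers the full Day 29 EOS list, which includes a dose and post-dose waits that no text exempts

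*Combined protocol and SAP*

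**What the plan says.** Three sections send an early stopper to the end-of-study procedures. Section 8.1, on stopping study treatment, says: "Procedures listed in the SoA for Part A check-out or Part B Day 29 EOS should be completed at the time of treatment discontinuation". Section 8 says that for a subject meeting a withdrawal criterion, "procedures listed in the SoA for Part A check-out or Part B Day 29 EOS will be required". The Section 8 reasons include pregnancy and "Grade 3 or 4 clinical AE considered causally related to treatment". Section 8.2 asks for the end-of-study procedures when a subject leaves the study.

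The Part B Day 29 list in Section 9 opens with questionnaires, VAS, MMP-9, TFBUT and staining at 0 h. It then has "Drug administration at 0 hour", laboratory tests at 2 h, and physical examination and vital signs at 4 h. Visual acuity, slit lamp, Schirmer, intraocular pressure and lens examination come at 8 h, and the list ends with "Ophthalmoscopy at 8 hours". VAS is repeated at 4 and 8 h.

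On follow-up off drug, Section 8 covers the subject who needs an interfering prohibited medicine: "If the subject is discontinued from study medication, they would remain in the study for safety assessments as needed". It adds: "Withdrawn subjects will not be replaced". Both co-primary efficacy endpoints in Section 10.4.1 are set at Day 29: eye dryness VAS (at 4 h) and central CFS.

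**The concern.** The list was written for a subject who is still on drug at Day 29. Carried over unchanged to a subject who has just been stopped, it brings a dose with it, and the later safety checks are timed from that dose. This matters most for the subjects whom Section 8 is there to protect: someone stopped for a related severe AE, or a pregnant subject. For an ocular reaction, the listed eye examinations would come 8 h into the visit when they are wanted at once.

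A smaller issue concerns efficacy data. A subject can stop drug and still consent, yet no text schedules a Day 29 VAS or central CFS off drug. Values not collected then cannot be recovered by any later analysis choice.

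**Working it through.** **Part 1: the dose.** No arithmetic applies, so the provisions are set side by side.

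| Provision | What it asks for | Exempts the dose or the waits? |
|---|---|---|
| Section 5.1 | EOS visit when a dosed subject stops or withdraws before Day 29 ±2 | No |
| Section 8 | Day 29 EOS procedures, mandatory once a withdrawal criterion is met | No |
| Section 8.1 | Day 29 EOS procedures when treatment stops | No |
| Section 8.2 | End-of-study procedures on leaving the study | No |
| Section 9, Day 29 EOS list | Dose at 0 h; safety checks at 2, 4 and 8 h | Not addressed |

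The table of changes at the front of the protocol gives the reason for the 2, 4 and 8 h times: those assessments were moved so that they follow dosing. Without a dose the times have no anchor. Section 9 also rules out waivers and exemptions, so a site that sensibly omits the dose departs from the written procedure. Section 9.2.1 still places the Day 29 eye examinations at 0 h, so the intended time is unclear as well. The Schedule of Activities has a drug administration row, but its columns do not line up in the text available to me; the 0 h dose is therefore taken from the Section 9 list. The fault is confined to Part B, because the Part A Day 2 list contains no dose.

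**Part 2: the efficacy gap.**

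*Timing.* A stop on Day 8, 15 or 22 puts the EOS procedures 29 − 8 = 21, 29 − 15 = 14 or 29 − 22 = 7 days early, outside the ±2-day window. The subject can still be in the Full analysis set, which needs one dose and one post-baseline efficacy measurement (Section 10.3).

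*Data lost per stopper.* Within a cohort, 1/20 = 5% of the active arm or 1/10 = 10% of the placebo arm. Section 10.4 also summarizes across active doses, where one active stopper is 1/40 = 2.5%.

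*Shift in the difference.* The protocol gives no dropout rate or SD. Assumptions: the stopper counts shown; stoppers' Day 29 dryness VAS change is X = 10 to 30 mm worse than the rest; SD 20 to 25 mm; only subjects with Day 29 data are summarized; the comparison is with a treatment-policy summary. Lower VAS is better. Each observed arm mean equals the full-arm mean minus p·X, where p is the fraction stopping, so

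shift in (active − placebo) = (p_placebo − p_active)·X, and SE = SD·√(1/n_active + 1/n_placebo), with n counting the subjects observed.

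| Stoppers, active vs placebo | Shift, mm | SE, mm |
|---|---|---|
| 0/20 vs 0/10 | 0 | 7.75 to 9.68 |
| 1/20 vs 0/10 | (0 − 0.05)·X = −0.5 to −1.5 | 7.81 to 9.77 |
| 0/20 vs 1/10 | (0.10 − 0)·X = +1 to +3 | 8.03 to 10.03 |
| 2/20 vs 1/10 | (0.10 − 0.10)·X = 0 | 8.16 to 10.21 |
| 2/20 vs 2/10 | (0.20 − 0.10)·X = +1 to +3 | 8.50 to 10.62 |
| 5/20 vs 1/10 (illustrative high case) | (0.10 − 0.25)·X = −1.5 to −4.5 | 8.43 to 10.54 |

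The largest ratio is 4.5/8.43 = 0.53 SE. It needs the high stopping imbalance, X = 30 and SD = 20 together. For central CFS with X assumed at 0.5 to 1 grade, the same formula gives shifts from −0.15 to +0.10 grade.

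**The case against.** **On the dose.** Section 8.1 is about stopping treatment, so dosing at that visit contradicts its purpose, and few sites would do it after a related severe AE. The eye examinations need not wait either: Appendix 4 obliges the investigator to arrange further evaluations when medically needed, and Section 9 calls for immediate safety concerns to be raised with the sponsor at once. This stands as to likely conduct. A reader might infer that the protocol intends to re-dose stopped subjects or to hold back their examinations; the documents do not support that. What they show is a cross-reference that lacks an exemption.

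**On the efficacy gap.** Most Section 8 reasons are reasons for leaving the study. The only group explicitly kept in the study off drug is subjects needing an interfering medicine, and that medicine would confound their Day 29 values. VAS and CFS are collected at the stopping visit and before it. The analysis is descriptive, and an on-treatment reading is legitimate and needs no off-drug values. All of this stands and keeps the gap narrow. Nor do the documents forbid later assessments: Section 8.1 lets the investigator decide whether a subject continues, and Section 9 stresses adherence to the schedule.

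**On completion.** Section 5.3 defines completion by "Day 2 EOS for Part A and Day 29 EOS for Part B", so a reader might infer that EOS procedures done early make a stopper a completer. The same sentence requires every phase to have been completed, and Section 5.1 separates the Day 29 ±2 visit from an EOS visit held at discontinuation. That inference fails.

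**On remaining visits.** A reader might also conclude that stoppers should attend every remaining visit. For a stop before Day 8 that would mean confinement off drug. It would also prolong the period in which Section 7.8.2 bars dry eye medicines and Section 7.8.3 provides no rescue. The case supports one visit at most.

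**Conclusion.** The first part holds on the text alone and depends on no dropout assumption: Sections 8, 8.1 and 8.2 import a dose and its post-dose timings into the stopping visit, with no exemption. It is a drafting fault that bears on subject safety, and it should be corrected even though sites would probably work around it.

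The second part is a secondary improvement. No text schedules a Day 29 efficacy assessment for a consenting subject who is off drug. Its effect is zero if all 60 complete, as Section 10.2 expects, and zero if stopping is proportionate between arms and stoppers differ by the same X in each. Otherwise it stays within about half a standard error under the assumed counts, X and SD. It applies only to a treatment-policy reading. A stronger claim of material bias in the efficacy result has no support in the documents, which supply none of the inputs it would need. Section 10.4 leaves further detail to a statistical analysis plan that is not in the text supplied, so the handling of missing data is not judged here.

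**What to change.** 1. **Correct the rule.** In Sections 8, 8.1 and 8.2, state that the EOS procedures at early discontinuation are done without study drug administration and without the post-dose waits, and that the ocular safety examinations are done promptly. The cost is wording only; who stops drug does not change.

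2. **Add one invited visit (secondary).** State that a subject who stops drug but still consents is invited, if willing and if it is safe, to the single Day 29 ±2 visit for VAS and central CFS without dosing. Flag these values as off-drug. Record any dry eye or other interfering therapy and allow it as clinically needed, with a matching line in Section 7.8.2. Pregnant subjects remain study withdrawals under Appendix 5. The cost is one already scheduled visit per affected subject. The downside is that an off-drug 4 h VAS has no preceding dose and is not like-for-like with on-drug values, so it should be reported separately or within a treatment-policy summary.

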8.2. Withdrawal from the Study

- A subject may withdraw from the study at any time at his/her own request or may be withdrawn at any time at the discretion of the investigator for safety, behavioral, compliance, or administrative reasons.
- If the subject withdraws consent for disclosure of future information, the sponsor may retain and continue to use any data collected before such a withdrawal of consent.
- If a subject withdraws from the study, he/she may request destruction of any samples taken and not tested, and the investigator must document this in the site study records.

- At the time of study discontinuation the End-of-Study procedures need to be completed.

8.3. Lost to Follow Up

A subject will be considered lost to follow-up if he or she repeatedly fails to return for scheduled visits and is unable to be contacted by the study site.

The following actions must be taken if a subject fails to return to the clinic for a required study visit:

- The site must attempt to contact the subject and reschedule the missed visit as soon as possible and counsel the subject on the importance of maintaining the assigned visit schedule and ascertain whether or not the subject wishes to and/or should continue in the study.
- Before a subject is deemed lost to follow up, the investigator or designee must make every effort to regain contact with the subject (where possible, 3 telephone calls and, if necessary, a certified letter to the subject's last known mailing address or local equivalent methods). These contact attempts should be documented in the subject's medical record.
- Should the subject continue to be unreachable, he/she will be considered to have withdrawn from the study with a primary reason of lost to follow-up.

9. Study Assessments and Procedures

- Study procedures and their timing are summarized in the SoA.
- Protocol waivers or exemptions are not allowed.
- Immediate safety concerns should be discussed with the sponsor immediately upon occurrence or awareness to determine if the subject should continue or discontinue study treatment.
- Adherence to the study design requirements, including those specified in the SoA, is essential and required for study conduct.
- Details for completion of each assessment will be included in the Study Manual.
- All screening evaluations must be completed and reviewed to confirm that potential subjects meet all eligibility criteria. The investigator will maintain a screening log to record details of all subjects screened and to confirm eligibility or record reasons for screening failure, as applicable.
- Procedures conducted as part of the subject's routine clinical management (eg, blood count) and obtained before signing of the ICF may be utilized for screening or baseline purposes provided the procedures met the protocol-specified criteria and were performed within the time frame defined in the SoA.

Table 9-1: Volume of Blood to be Collected from Each Subject

Type of Sample	Volume per Sample (mL)	No. of Samples/ Subject		Total Volume of Blood (mL) ^a	
		Part A	Part B	Part A	Part B
Safety (including screening and post treatment assessments)					
- Hematology	4.0	3	4	12.0	16.0
- Serum chemistry	8.5	3	4	25.5	34.0
serology (HIV, HBsAg, HCV)	8.5	1	1	8.5	8.5
serum β-hCG pregnancy test (WOCBP only)	4.9	1	2	4.9	9.8
Pharmacokinetic samples	2.0	8	9	16.0	18.0
Loss by use of indwelling intravenous cannula	1.0	8	9	8.0	9.0
Total				74.9	95.3

^a Calculated as number of samples multiplied by amount of blood per sample.

Note: An indwelling intravenous cannula may be used for blood sample collection. If a mandarin (obturator) is used, blood loss due to discard is not expected.

- If blood samples are collected via an indwelling cannula, an appropriate amount (i.e., 1 mL) of fluid slightly greater than the dead space volume of the lock will be removed from the cannula and discarded before each blood sample is taken. After blood sample collection, the cannula will be flushed with saline and charged with a volume equal to the dead space volume of the lock.
- The approximate amount of blood collected from subjects in Part A and Part B will be 75 mL and 95 mL, respectively. Repeat or unscheduled samples may be taken for safety reasons or for technical issues with the samples.

Daily Procedures – Part A

Screening (Day -30 to Day -15)

- Sign ICF
- Record medical and medication history and demographic information (age, sex, race, iris color)
- Review inclusion/exclusion criteria
- Physical examination
- Height (cm) and weight (kg)
- Vital signs
- DEQ-5
- VAS
- OSDI
- Clinical laboratory tests (hematology, serum chemistry, urinalysis)
- Serology (HIV, HBsAg, HCV)
- Serum pregnancy test for WOCBP; FSH for post-menopausal women
- Urine drug and alcohol screens
- Visual acuity (Snellen)
- Slit lamp biomicroscopy (w/out mydriatics)
- MMP-9 (30 minutes before TFBUT and staining tests)
- TFBUT
- Corneal fluorescein staining (Baylor)
- Lissamine green (Baylor + Lid Margin)
- Aesthesiometer
- Schirmer I without anesthesia
- VAS with anesthesia

- Intraocular Pressure (iCare tonometer)
- Slit lamp biomicroscopy (w/ mydriatics; lens observation)
- Ophthalmoscopy

Run-in (Day -14 +2 to Day -2)

- Educate subject in self-administration and dosing diary completion
- Dispense placebo. Subjects will instill one drop in each eye [REDACTED] (First dose may be administered in office as part of self-administration education, if visit is completed on Day -14, otherwise subject should be instructed to begin dosing on Day -14.)
- Review AEs and concomitant medications

Day -1 (Check-in)

- Review medical and medication history
- Review inclusion/exclusion criteria
- Weight
- Vital signs
- DEQ-5
- VAS
- OSDI
- Clinical laboratory tests (hematology, serum chemistry, urinalysis)
- Urine drug and alcohol screens
- Urine pregnancy test for WOCBP
- Visual acuity (Snellen)
- MMP-9 (30 minutes before staining tests)
- Corneal fluorescein staining (Baylor)
- Schirmer I without anesthesia
- Slit lamp biomicroscopy (w/ mydriatics; lens observation)
- Ophthalmoscopy
- Review AEs and concomitant medications
- Administer placebo [REDACTED] as during run-in

Day 1, Predose

- Review AEs and concomitant medications
- Physical examination

- Vital signs
- VAS
- PK sampling
- Slit lamp biomicroscopy (without mydriatics)
- TFBUT
- Corneal fluorescein staining (Baylor)
- Lissamine green (Baylor + Lid Margin)
- Intraocular Pressure (iCare tonometer)
- Randomize to study treatment

Day 1, 0 hour

- Administer study drug

Day 1, Postdose

- Review AEs and concomitant medications
- Physical examination at 1 hour
- Vital signs at 0.5, 1, 2, 4, 8, and 12 hours
- VAS at 0.5, 1, 2, 4, 8, and 12 hours
- PK sampling at 0.25, 0.5, 1, 2, 4, 8, and 12 hours
- Visual acuity at 12 hours
- Slit lamp biomicroscopy (without mydriatics) at 1, 2, and 12 hours
- TFBUT at 2 and 12 hours
- Corneal fluorescein staining (Baylor) at 2 and 12 hours
- Schirmer I without anesthesia at 12 hours
- Intraocular Pressure (iCare tonometer) at 2 and 12 hours
- Slit lamp biomicroscopy (w/ mydriatics; lens observation) at 12 hours
- Ophthalmoscopy at 12 hours

Day 2, 24 hours Postdose

- Review AEs and concomitant medications
- Physical Examination
- Vital signs
- VAS

- Clinical laboratory tests (chemistry, hematology, urinalysis)
- Visual Acuity (Snellen)
- Slit lamp biomicroscopy (w/out mydriatics)
- TFBUT
- Corneal fluorescein staining (Baylor)
- Schirmer I w/o anesthesia
- Intraocular Pressure (iCare tonometer)
- Slit lamp biomicroscopy (w/ mydriatics; lens observation)
- Ophthalmoscopy
- Check-out of clinic

Part B

Screening (Day -30 to Day -15)

- Sign ICF
- Record medical and medication history and demographic information
- Review inclusion/exclusion criteria
- Physical examination
- Height (cm) and weight (kg)
- Vital signs
- DEQ-5
- VAS
- OSDI
- Clinical laboratory tests (hematology, serum chemistry, urinalysis)
- Serology (HIV, HBsAg, HCV)
- Serum pregnancy test for WOCBP; FSH for post-menopausal women
- Urine drug and alcohol screens
- Visual acuity (Snellen)
- Slit lamp biomicroscopy (w/out mydriatics)
- MMP-9 (30 minutes before TFBUT and staining tests)
- TFBUT

- Corneal fluorescein staining (Baylor)
- Lissamine green (Baylor + Lid Margin)
- Aesthesiometer
- Schirmer I without anesthesia
- VAS with anesthesia
- Intraocular Pressure (iCare tonometer)
- Slit lamp biomicroscopy (w/ mydriatics; lens observation)
- Ophthalmoscopy

Run-in (Day -14 +2 to Day -2)

- Educate subject in self-administration and dosing diary completion
- Dispense placebo. Subjects will instill one drop in each eye [REDACTED] (First dose may be administered in office as part of self-administration education, if visit is completed on Day -14, otherwise subject should be instructed to begin dosing on Day -14)
- Review AEs and concomitant medications

Day -1 (Check-in)

- Review medical and medication history
- Review inclusion/exclusion criteria
- Weight
- Vital signs
- DEQ-5
- VAS
- OSDI
- Clinical laboratory tests (hematology, serum chemistry, urinalysis)
- Urine drug and alcohol screens
- Urine pregnancy test for WOCBP
- Visual acuity (Snellen)
- MMP-9 (30 minutes before staining tests)
- Corneal fluorescein staining (Baylor)
- Schirmer I without anesthesia
- Slit lamp biomicroscopy (w/ mydriatics; lens observation)
- Ophthalmoscopy

- Review AEs and concomitant medications
- Administer placebo [REDACTED] as during run-in

Day 1, Predose

- Review AEs and concomitant medications
- Physical examination
- Vital signs
- VAS
- PK sampling
- Slit lamp biomicroscopy (without mydriatics)
- TFBUT
- Corneal fluorescein staining (Baylor)
- Lissamine green (Baylor + Lid Margin) at 12 hours
- Intraocular Pressure (iCare tonometer)
- Randomize to study treatment

Day 1, 0 hour

- Administer study drug

Day 1, Postdose

- Review AEs and concomitant medications
- Physical examination at 1 hour
- Vital signs at 0.5, 1, 2, 4, 8, and 12 hours
- VAS at 0.5, 1, 2, 4, 8, and 12 hours
- PK sampling at 0.25, 0.5, 1, 2, and 4 hours
- Visual acuity at 12 hours
- Slit lamp biomicroscopy (without mydriatics) at 1, 2, and 12 hours
- TFBUT at 2 and 12 hours
- Corneal fluorescein staining (Baylor) at 2 and 12 hours
- Lissamine green (Baylor + Lid Margin) at 12 hours
- Schirmer I without anesthesia at 12 hours
- Intraocular Pressure (iCare tonometer) at 12 hours
- Slit lamp biomicroscopy (w/ mydriatics; lens observation) at 12 hours

- Ophthalmoscopy at 12 hours
- Administer study drug at 4, 8, and 12 hours

Days 2 and 3

- Review AEs and concomitant medications
- Physical examination at 0 hour
- Vital signs at 0, 4, 8, and 12 hours
- VAS at 0, 4, 8, and 12 hours
- Visual acuity at 0 hours
- PK sampling at predose on Day 2 (ie, Day 1, 24 hours)
- Slit lamp biomicroscopy (without mydriatics) at 0 and 12 hours
- TFBUT at 0 and 12 hours
- Corneal fluorescein staining (Baylor) at 0 and 12 hours
- Lissamine green (Baylor + Lid Margin) at 0 and 12 hours
- Schirmer I without anesthesia at 0 hours on Day 2
- Intraocular Pressure (iCare tonometer) at 0 hour
- Administer study drug at 0, 4, 8, and 12 hours

Days 4 through 7

- Review AEs and concomitant medications
- Physical examination at 0 hour
- Vital signs at 0 hour
- VAS on Day 4 and on Day 7 at 0, 0.5, 1, 2, 4, 8, and 12 hours; VAS on Days 5 and 6 at 0, 4, 8, and 12 hours
- PK sampling at 0 hour on Day 4
- Visual acuity at 0 hours
- Slit lamp biomicroscopy without mydriatics at 0 and 12 hours
- TFBUT at 0 and 12 hours
- Corneal fluorescein staining (Baylor) at 0 and 12 hours
- Lissamine green staining (Baylor +Lid Margin) at 0 and 12 hours
- Administer study drug at 0, 4, 8, and 12 hours

Day 8, Check Out

- Review AEs and concomitant medications

- Physical examination at 0 hour
- Vital signs at 0 hour
- VAS at 0 hour
- OSDI at 0 hour
- PK sampling at 0 hour
- Clinical laboratory tests (hematology, serum chemistry, urinalysis) at 0 hour
- Visual Acuity (Snellen) at 0 hour
- Slit lamp biomicroscopy without mydriatics at 0 hour
- TFBUT at 0 hour
- Corneal fluorescein staining (Baylor) at 0 hour
- Lissamine green staining (Baylor +Lid Margin) at 0 hour
- Schirmer I without anesthesia at 0 hour
- Intraocular pressure (iCare tonometer) at 0 hour
- Slit lamp biomicroscopy w/ mydriatics (lens observation) at 0 hour
- Ophthalmoscopy at 0 hour
- Administer study drug at 0 hour
- Dispense study drug for administration at home
- Dispense diary and complete refresher education on completion of diary and self-administration of study drug
- Discharge subjects from clinic
- Subjects self-administer study drug at 0, 4, 8, and 12 hours each day
- Subjects record dosing times in diary

Day 9 through Day 28

- Subjects self-administer study drug at 0, 4, 8, and 12 hours each day
- Subjects record dosing times in diary

Day 15 ±2 and Day 22 ±2

Subjects come to clinic for the following assessments (at 0 hour unless otherwise noted):

- Review AEs and concomitant medications
- Physical examination at 0 hour
- Vital signs at 0 hour
- VAS at 0, 4, and 8 hours

- OSDI at 0 hour
- Visual acuity at 0 hour
- Slit lamp biomicroscopy w/out mydriatics at 0 hour
- TFBUT at 0 hour
- Corneal fluorescein staining (Baylor) at 0 hour
- Lissamine green staining (Baylor +Lid Margin) at 0 hour
- Intraocular Pressure (iCare tonometer) at 0 hour
- Subjects self-administer study drug at 0, 4, 8, and 12 hours each day
- Subjects record dosing times in diary
- Dispense study drug for administration at home

Day 29 ±2, EOS

- Review AEs and concomitant medications
- DEQ-5 at 0 hour
- VAS at 0, 4, and 8 hours
- OSDI at 0 hour
- MMP-9 at 0 hour (30 minutes before TFBUT and staining tests)
- TFBUT at 0 hour
- Corneal fluorescein staining (Baylor) at 0 hour
- Lissamine green staining (Baylor +Lid Margin) at 0 hour
- Drug administration at 0 hour
- Clinical laboratory tests (hematology, serum chemistry, urinalysis) at 2 hours
- Serum pregnancy test for WOCBP only at 2 hours
- Physical examination, including weight at 4 hours
- Vital signs at 4 hours
- Visual Acuity (Snellen) at 8 hours
- Slit lamp biomicroscopy without mydriatics at 8 hour
- Schirmer I without anesthesia at 8 hours
- Intraocular pressure (iCare tonometer) at 8 hours
- Slit lamp biomicroscopy w/ mydriatics (lens observation) at 8 hours
- Ophthalmoscopy at 8 hours

Day 36 ±2

- Follow-up telephone call to review AEs and concomitant medications

